### **6.1.7 Excluded Treatments, Medical Devices, and/or Procedures During Study Period**

Any anti-tumor therapy other than the investigational product, including cytotoxic and/or cytostatic drugs, hormonal therapy, systemic corticosteroids (except for subjects who were receiving  $\leq 10$  mg prednisone or equivalent at the time of enrollment are permitted to remain on it), immunotherapy or any biological response modifiers, any other investigational agent, and other immunosuppressive therapies are excluded.

Primary prophylactic use of hematopoietic growth factors such as granulocyte-colony stimulating factor is not encouraged during the DLT-evaluation period. Once the DLT evaluation period is complete, the use of growth factors can be allowed after discussion with the Amgen medical monitor.

Administration of systemic corticosteroids, immunomodulators, and hormonal replacement therapy for the management of toxicities (eg, immune-related adverse events) is allowed; however, AMG 994 and AMG 404 must be discontinued if  $\geq 10$  mg per day prednisone or equivalent is continued for more than 12 weeks. Corticosteroids with no or minimal systemic effect (eg, topical, inhalation) are allowed.

Any live vaccine therapies for the prevention of infectious disease are not allowed (except administration of the inactive influenza vaccine).

Radiotherapy is not permitted except for palliation of symptoms and should be discussed with the sponsor's Medical monitor first. Investigators should ensure that the need for radiation does not indicate progressive disease and that for subjects with measurable disease, radiation is not to the sole site of measurable disease.

The following procedures should also not be undertaken within the timeframes specified prior to enrollment and during the study:

- Participation in any investigational study (drug or device) within [REDACTED]  
[REDACTED]
- Major surgery within [REDACTED]
- Enrollment into another investigational drug or device study

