#### **6.2.2.2 Rules for Withholding or Restarting**

- AMG 994, and AMG 404 if the subject is on combination therapy, should be withheld for any DLT or any adverse event that meets the criteria of a DLT but occurs outside of the DLT windows
- AMG 994, and AMG 404 if the subject is on combination therapy, should be withheld for potential hepatotoxicity as detailed in [Table 11-2](#)
- AMG 404 alone should be withheld for immune-mediated adverse reactions as detailed in [Table 11-3](#)
- AMG 994 and/or AMG 404 should be withheld for infusion-related reactions as specified in [Table 11-4](#)

For adverse events not addressed by [Table 11-2](#), [Table 11-3](#) and [Table 11-4](#), AMG 994 and AMG 404 dosing can be resumed if the applicable event resolves to grade  $\leq 1$  or otherwise resolves to subject's baseline grade within 2 weeks. The restarting of therapy should be deemed appropriately safe by the investigator and Medical Monitor. For restart criteria following hepatotoxicity, immune-mediated reactions, and infusion-related reactions, refer to [Table 11-2](#), [Table 11-3](#) and [Table 11-4](#), respectively. For immune-mediated hepatitis, if [Table 11-2](#) and [Table 11-3](#) are both applicable, [Table 11-2](#) is to take precedence.

Subjects should not be restarted with AMG 994 and/or AMG 404 if the following treatment-related adverse events occur:

- Any grade 4 adverse events except those not considered DLT, OR
- Adverse event criteria are met for permanent withholding of AMG 994 and/or AMG 404 due to potential hepatotoxicity, immune-mediated reaction or infusion related reaction ([Table 11-2](#), [Table 11-3](#), or [Table 11-4](#), respectively). For immune-mediated hepatitis, if [Table 11-2](#) and [Table 11-3](#) are both applicable, [Table 11-2](#) is to take precedence.

If a subject experiences an adverse event meeting withholding or discontinuation criteria above from AMG 404, and if the subject is experiencing clinical benefit with AMG 994 monotherapy, a decision to have the subject continue with AMG 994 monotherapy alone, may be considered by the Amgen medical monitor in consultation with the investigator.

The reason for dose change of AMG 994 and/or AMG 404 is to be recorded on each subject's CRF.

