Hypophysitis	Grade 3 or 4 not responsive to therapy within 2 days	Permanently discontinue	Administer corticosteroids at an initial dose of 1 mg/kg/d prednisone (or equivalent) followed by taper. In addition, initiate hormonal replacement therapy as clinically indicated.	Monitor for signs and symptoms of hypophysitis. Consider endocrine consultation.
Adrenal Insufficiency	Grade 3 or 4 not responsive to therapy within 2 days	Permanently discontinue	Initiate IV stress-dose corticosteroids on presentation (hydrocortisone 100 mg or dexamethasone 4 mg [if the diagnosis is not clear and ACTH stimulation testing will be needed]). Taper stress-dose corticosteroids down to maintenance doses (prednisone 5 to 10 mg daily) over 1-2 weeks after discharge.	Monitor for signs and symptoms of adrenal insufficiency. Consider endocrine consultation.
Hypothyroidism	Grade 3 or 4 not responsive to therapy within 2 days	Permanently discontinue	Initiate thyroid hormone supplementation.	Monitor subjects for signs and symptoms of hypothyroidism. Consider endocrine consultation.
Hyperthyroidism	Grade 3 or 4 not responsive to therapy within 2 days	Permanently discontinue	Initiate $\beta$ -Blocker (eg, atenolol, propranolol) for symptomatic relief. For severe symptoms or concern for thyroid storm, initiate prednisone 1-2 mg/kg/d (or equivalent) tapered over 1-2 weeks. Consider use of potassium iodide (SSKI)	Monitor subjects for signs and symptoms of hyperthyroidism. Consider endocrine consultation.

**Product:** AMG 994 and AMG 404

**Protocol Number:** 20190136

**Date:** 16 June 2022

Page 167 of 180

		or thionamide (methimazole or propylthiouracil [PTU]).	
--	--	--	--

Page 4 of 8

Footnotes defined on last page of this table

**Table 11-3. Dose Modification and Toxicity Management Guidelines for Immune-related Adverse Reactions Associated With AMG 404\***

Immune-related Adverse Reactions	Severity (CTCAE Grade Version 5.0 or Specific Conditions)	AMG 404 Dose Modification	Management with Corticosteroids and/or Other Therapies	Monitor & Follow-up	
Diabetes Mellitus	Grade 3 not responsive to therapy within 2 days	Permanently discontinue	Initiate insulin therapy.	Monitor subjects for hyperglycemia or other signs and symptoms of diabetes. Consider endocrine consultation.	
	Grade 4 hyperglycemia (> 500 mg/dL [ $> 27.8 \text{ mmol/L}$ ])				

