**AMGEN®**

**Table 11-3. Dose Modification and Toxicity Management Guidelines for Immune-related Adverse Reactions Associated With AMG 404\***

Immune-related Adverse Reactions	Severity (CTCAE Grade Version 5.0 or Specific Conditions)	AMG 404 Dose Modification	Management with Corticosteroids and/or Other Therapies	Monitor & Follow-up		
Myocarditis	Grade 1 (abnormal cardiac biomarker testing, including abnormal ECG)	Withhold	Administer corticosteroids at an initial dose of 1 to 2 mg/kg/d prednisone (or equivalent) followed by taper.	Monitor patients with cardiovascular symptoms. Ensure adequate evaluation to confirm etiology and/or exclude other causes.		
	Grade 2 (abnormal screening tests with mild symptoms)					
	Grade 3 (moderately abnormal testing or symptoms with mild activity)	Permanently discontinue				
	Grade 4 (moderate to severe decompensation, IV medication or intervention required, life-threatening conditions)					
All Other Immune-Related Adverse Reactions	Grade 3 adverse reaction involving a major organ	Withhold	Based on type and severity of adverse reaction, administer corticosteroids. Refer to ASCO Clinical Practice Guidelines for additional recommendations.	Ensure adequate evaluation to confirm etiology and/or exclude other causes.		
	Life-threatening or Grade 4 adverse reaction involving a major organ	Permanently discontinue				

Page 7 of 8

Footnotes defined on last page of this table

**Table 11-3. Dose Modification and Toxicity Management Guidelines for Immune-related Adverse Reactions Associated With AMG 404\***

Immune-related Adverse Reactions	Severity (CTCAE Grade Version 5.0 or Specific Conditions)	AMG 404 Dose Modification	Management with Corticosteroids and/or Other Therapies	Monitor & Follow-up
Recurrent or Persistent Immune-Related Adverse Reactions	Recurrence of same Grade 3 or Grade 4 adverse reaction	Permanently discontinue	Based on type and severity of adverse reaction, administer corticosteroids. Additional immunosuppressive treatment may be required.	Ensure adequate evaluation to confirm etiology and/or exclude other causes.
	Requirement for $\geq 10$ mg/day prednisone (or equivalent) for more than 12 weeks			
	Persistent grade 2 or 3 adverse reactions lasting 12 weeks or longer after last dose (ie, does not resolve to grade 0 or 1 within 12 weeks)			

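### Prednisone ≥10 mg/day for toxicity beyond 12 weeks: Protocol 6.1.7 stops both drugs, Table 11-3 stops AMG 404 only, and 6.2.2.2 leaves AMG 994 alone as an option, with no stated precedence

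*Protocol*

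**What the plan says.** Three parts of the Protocol deal with prolonged corticosteroids given for toxicity.

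- **Section 6.1.7 (excluded treatments).** Steroids for toxicity are allowed, but "AMG 994 and AMG 404 must be discontinued if" ≥10 mg per day "prednisone or equivalent is continued for more than 12 weeks". The rule is mandatory and names both drugs. The same section says that subjects already taking ≤10 mg "prednisone or equivalent at the time of enrollment are permitted to remain on it".
- **Section 11.10, Table 11-3, Recurrent or Persistent Immune-Related Adverse Reactions.** One of three triggers is a need for ≥10 mg/day "prednisone (or equivalent) for more than 12 weeks". The action is permanent discontinuation, in a column that covers AMG 404 dose modification only.
- **Section 6.2.2.2 (withholding and restarting).** "AMG 404 alone should be withheld for immune-mediated adverse reactions as detailed in" Table 11-3. Later, for a subject who "experiences an adverse event meeting withholding or discontinuation criteria above from AMG 404" and is benefiting from AMG 994 monotherapy, the text says that "a decision to have the subject continue with AMG 994 monotherapy alone, may be considered by the Amgen medical monitor", after consulting the investigator.

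The adrenal insufficiency row of Table 11-3 requires permanent discontinuation for "Grade 3 or 4 not responsive to therapy within 2 days". It directs a taper to maintenance prednisone of 5 to 10 mg daily and gives no end date. Where AMG 404 has been withheld, Section 6.2.2.1 and the general considerations of Table 11-3 allow restart only once prednisone is below 10 mg.

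**The concern.** A site managing an immune-mediated reaction will look in 6.2.2.2 and Table 11-3, and neither refers back to 6.1.7. A site that reads 6.1.7 must stop AMG 994. A site that reads the other two texts may ask to continue it alone. The drug in question is the first-in-human agent, so the same clinical situation should not end differently according to which section was opened.

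The adrenal row raises a smaller problem. A subject whose adrenal insufficiency is controlled on the table's own maintenance dose can, at the top of that range, meet a stopping rule that the adrenal row itself does not impose.

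**Working it through.** No plan figure needs reproducing. The check is a comparison of texts plus one threshold calculation.

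**1. Trigger and action side by side**

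| Text | Trigger | AMG 404 | AMG 994 |
|---|---|---|---|
| 6.1.7 | ≥10 mg/day, more than 12 weeks, given for toxicity | Must stop | Must stop |
| Table 11-3, Recurrent or Persistent | ≥10 mg/day, more than 12 weeks | Permanently stop | Not mentioned |
| 6.2.2.2 | AMG 404 withholding or discontinuation criteria met | As Table 11-3 | May continue alone if benefiting; medical monitor decides |

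Dose and duration are identical in the first two rows. Only the drugs covered differ.

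**2. Does the monotherapy option reach this trigger?** Yes. The criteria it refers back to include permanent withholding under Table 11-3, and the steroid-duration trigger sits in that table under permanent discontinuation. The option makes no exception for it.

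**3. Is there a precedence rule?** Only one, stated twice in 6.2.2.2: Table 11-2 outranks Table 11-3 for immune-mediated hepatitis. Nothing ranks 6.1.7 against 6.2.2.2 or Table 11-3.

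**4. Which subjects are left?** The first bullet of 6.2.2.2 withholds AMG 994 for any DLT and for any event that meets DLT criteria outside the window. The criteria in 6.2.1 include grade 3 or 4 non-hematologic toxicity (with listed exceptions) and recurrent grade 2 pneumonitis. Many reactions needing 12 weeks of prednisone would already have led to withholding by this route. The divergence therefore bears mainly on persistent events below those criteria.

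**5. Adrenal threshold.** Maintenance is 5 to 10 mg daily, the trigger is ≥10 mg, and restart needs <10 mg.

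| Maintenance dose | 12-week stop met? | AMG 404 restart allowed on dose? |
|---|---|---|
| 5 to below 10 mg | No | Yes |
| Exactly 10 mg | Yes, after 12 × 7 = 84 days | No |

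The overlap is the single value 10 mg/day. Two nearby allowances do not remove it. The ≤10 mg allowance in 6.1.7 concerns steroids already taken at enrollment, and the mention of physiologic steroid doses in inclusion criterion 108 concerns eligibility with brain metastases.

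**The case against.** The best reply is that the texts can be obeyed together. Section 6.1.7 is mandatory, Table 11-3 is silent on AMG 994, and the monotherapy option is only discretionary. Stopping both drugs breaches nothing, so all that is missing is a cross-reference. The option is also narrow: it needs a medical monitor decision and benefit from AMG 994 monotherapy, whereas Part 2 gives the combination from cycle 1 day 1.

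Much of this stands. Continuation is never automatic, and a careful reader would probably treat the mandatory sentence as controlling. But the Protocol does not say that it controls. Section 6.2.2.2 expressly opens the other route after AMG 404 discontinuation criteria are met, and Section 6.2.2.1 supplies a rationale for sparing AMG 994 by expecting immune-mediated reactions to be associated with AMG 404. Where the authors wanted one text to prevail, as for hepatitis, they said so.

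On the adrenal point, it is fair to reply that a dose below 10 mg avoids the problem, and that an allowance for steroids taken before the study is no precedent for prolonged steroids given for toxicity. Those replies make it an edge case. They do not remove the inconsistency at 10 mg, a dose that the table itself offers.

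**Conclusion.** The inconsistency holds in the current text and does not arise from redaction. One trigger carries a mandatory stop of both drugs in one section and a possible continuation of AMG 994 under two others, with no precedence stated. It is a modest problem of consistent safety management. How many subjects would be affected cannot be derived from the documents. The adrenal overlap is secondary and confined to 10 mg/day.

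Three stronger inferences are not supported.

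- **That DLT rates would shift.** More than 12 weeks of steroid means day 85 at the earliest. The DLT windows are redacted. If there are two of one 28-day cycle each (an assumption), they end by day 56, which is 85 − 56 = 29 days earlier. A window would have to reach the fourth 28-day cycle to capture such a stop. SAP 9.6.2 limits the primary DLT analysis to events inside the evaluation period.
- **That the drug-scope conflict changes the count of adverse events requiring permanent discontinuation.** Table 11-3 already stops AMG 404 permanently on this trigger, and SAP 9.6.2 lists no separate tables by drug. No clear change follows.
- **That most AMG 994 treatment is at stake.** Subtracting 12 weeks from the maximum durations gives 40 of 52 weeks (77%) for a complete response and 92 of 104 weeks (88%) for a partial response or stable disease. Those are ceilings that require qualifying steroids from day 1 and treatment otherwise running to the maximum. In sequential cohorts AMG 404 starts only in cycle 2, so a reaction to it could not reach the limit at day 85. They are not expected losses.

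**What to change.** Keep the mandatory both-drug rule in 6.1.7, which is the existing and more cautious position for a first-in-human agent, and bring the other texts into line.

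1. **Section 6.2.2.2, monotherapy paragraph:** add *except when the 12-week corticosteroid limit in Section 6.1.7 is met*.
2. **Table 11-3, Recurrent or Persistent row, against the steroid-duration trigger only:** add *also discontinue AMG 994, see Section 6.1.7*. It must not attach to the row's other two triggers (recurrence of the same grade 3 or 4 reaction, and persistent grade 2 or 3 reactions), for which 6.1.7 requires no AMG 994 stop.
3. **Section 6.1.7 and the same Table 11-3 trigger:** state that *physiologic adrenal replacement (prednisone up to 10 mg daily or equivalent) does not count toward the 12-week limit*.
4. **Restart conditions in Section 6.2.2.1 and the Table 11-3 general considerations:** state that the same replacement dosing does not bar restart.

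The cost is wording in Sections 6.1.7, 6.2.2.1, 6.2.2.2 and Table 11-3 at the next amendment. There are no added visits, procedures or subjects, and the SAP does not change. The one downside is that discretionary continuation of AMG 994 is explicitly closed for this trigger. If the sponsor prefers to keep it open, 6.1.7 would have to be changed instead; either way the sections need to say the same thing.

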### **6.2 Dose Modification**

#### **6.2.1 Dose-cohort Study Escalation/De-escalation and Stopping Rules**

[figure not shown]
##### **Sentinel Dosing**

[figure not shown]
During the dose-exploration part of the study, there will be at least a 1-week interval between start of treatment of the first and second subject, in each cohort (ie, at the same

dose for AMG 994 monotherapy and AMG 994 in combination with AMG 404). Prior to start of a new subject, the site investigator of the previous subject will evaluate all available safety and laboratory data for the treated subject and will send written confirmation on occurrence/non-occurrence of a DLT to the sponsor. The sponsor will only be able to approve treatment start for the next subject in the cohort after receipt of this confirmation. If deemed necessary, the 1-week interval may be extended until sufficient data are available to allow an assessment of the feasibility of treatment start of the next subject. In addition to the 1-week interval between treatment start of the first and second subject in each cohort, there will be a 72-hour interval between treatment start of the second and third subject, then all subsequent subjects in each cohort may start treatment. Sentinel dosing may apply during cohort extension, at the Sponsor's discretion, based on available safety data. The same process as described above will apply for determining if subsequent subjects may start treatment.

[figure not shown]
#### **DLT-evaluable Periods (DLT Windows)**

Part 1a will include [REDACTED] of 3 to 6 subjects each.

[figure not shown]

Part 1b:

Part 1c:

### **Dose Level Determination**

A recommendation to escalate to a higher dose cohort will only occur when the previous dose regimen has been found to be reasonably tolerated based on available study data through study [REDACTED] of cycle 1 for all evaluable subjects and upon unanimous agreement of the DLRT members. Available data from previous cohorts will also be considered. Dose level recommendations will be made on a treatment cohort basis (not on an individual basis). After receiving the DLRT recommendation, Amgen will render a final decision and will issue a written notification of the dose change decision to

investigators. Further information on dose level review meetings is provided in Appendix 3 (Section 11.3).

After all DLT-evaluable subjects have completed the monotherapy DLT window, the first DLRM will be held to review data, monitor safety, and recommend dose changes, if applicable. [REDACTED]

[REDACTED]  
[REDACTED].  
The review team will be composed of the investigators, Amgen Medical Monitor, Amgen Global Safety Officer (GSO) or designated safety scientist, Amgen Early Clinical Development Manager, and Biostatistics representative. Additional members may be added as needed (eg, Clinical Pharmacologist). The Medical Monitor must be in attendance and cannot be represented by a voting designee or delegate. Voting designees can be identified as appropriate by the GSO or site investigators.

A quorum, defined as the majority (defined as greater than or equal to 50%) of actively screening and enrolling investigators or their qualified designee (ie, sub-investigator), must be in attendance for DLRM to proceed. The DLRM will be rescheduled if a quorum is not reached.

Voting members of the DLRM will include the Amgen Medical Monitor, the Amgen GSO or designated safety scientist, and all actively screening and enrolling investigators or their qualified sub-investigator designee. The team may recommend escalation to the next planned dose, escalation to an intermediate dose (a dose lower or higher than the next planned dose), continuation or delay in dosing, repetition or expansion of a cohort, de-escalation to a lower dose, or termination of the study. One or more dosing regimens may be selected based on clinical findings including safety, tolerability, and PK results from previous cohorts; after DLRT review, the DLRT may make recommendations for the next cohort dose and frequency. [REDACTED]

[REDACTED]. The Amgen Medical Monitor and GSO or designee and the majority (defined as greater than or equal to 50%) of actively screening and enrolling investigators participating in the DLRM must cast a positive vote indicating an acceptable safety profile was observed for AMG 994 to allow the dose level modification and/or cohort continuation/expansion to proceed. All available study data including demographics, medical history, concomitant medications,

AEs, ECGs, vital signs, laboratory results, and emerging PK or pharmacodynamics data will be reviewed. Data to be reviewed may be unqueried.

The dosing schedule is described by the Study Schema in the protocol synopsis (see Section 1.2).

### **Dose Cohort Stopping Rules**

The DLRT will recommend escalation to the next planned dose, escalation to an intermediate dose (a dose lower or higher than the next planned dose), continuation or delay in dosing, repetition or expansion of a cohort, de-escalation to a lower dose, or termination of the study. One or more dosing regimens may be selected based on clinical findings including safety, tolerability, and PK results from previous cohorts; after DLRT review, the DLRT may make recommendations for the next cohort dose and frequency. [REDACTED]

[REDACTED] All available study data including demographics, medical history, concomitant medications, AEs, ECGs, vital signs, laboratory results, and emerging PK or pharmacodynamics data will be reviewed.

The Amgen Medical Monitor may suspend dosing and convene a DLRM at any time based on emerging safety data.

The study may be terminated at any point at the discretion of the sponsor.

### **Dose-Limiting Toxicity**

All events will be graded using the CTCAE version 5.0. The occurrence of any of the following events during the first or second DLT evaluation period will be considered a DLT, excluding events clearly related to disease progression or intercurrent illness:

- Any grade 5 event
- Grade 4 neutropenia or thrombocytopenia of any duration
- Grade 3 thrombocytopenia with clinically significant bleeding or lasting > 7 days
- Febrile neutropenia
- Grade 4 anemia
- Grade 3 or 4 non-hematologic toxicity, with the following exceptions:
  - DLT Exemption: Grade 3 nausea/vomiting or diarrhea < 72 hours in the absence of maximal medical therapy
  - DLT Exemption: Grade 3 fatigue < 1 week

- DLT Exemption: Asymptomatic grade 3 electrolyte abnormalities that last < 72 hours, are not clinically complicated, and resolve spontaneously or respond to conventional medical interventions
- DLT Exemption: Grade 3 amylase or lipase elevations, as per CTCAE version 5.0, grade 4 elevations in amylase and lipase are defined as being associated with signs or symptoms of pancreatitis
- DLT Exemption: Other laboratory parameters of grade 3, not considered clinically relevant, and improved to grade  $\leq 2$  within 72 hours.
- Any grade 3 event requiring hospitalization
- Recurrent grade 2 pneumonitis
- Delay in cycle 2 treatment for  $> 14$  days due to an adverse event in the dose escalation portion of the study due to study drug-related toxicity, except for immune-mediated toxicities as outlined in [Table 11-3](#) where a longer timeframe is specified
- Any other event requiring permanent discontinuation of AMG 994 (for example, as specified in [Table 11-4](#), Infusion-Related Reactions)

[figure not shown]
The cumulative adverse event profile will be taken into consideration when making decisions on dose escalation and on any other dose-level or safety review.

Any subject meeting the criteria for Hy's Law case (ie, severe drug-induced liver injury) will be considered a DLT. A Hy's Law case is defined as: AST or ALT values of  $\geq 3 \times$  ULN AND with serum TBL of  $> 2 \times$  ULN without signs of cholestasis and with no other clear alternative reason to explain the observed liver-related laboratory abnormalities (see Section [6.2.3](#) for hepatotoxicity management and Section [11.7](#) for further explanation of Hy's law case and Management of Hepatic Function).

Clinically or medically significant suspected adverse drug reactions, and serious adverse events considered to be related to study procedures will be followed until resolved or considered stable.

The study may be terminated at any point at the discretion of the sponsor.

The DLT window (ie, DLT-evaluable period) during dose exploration will start on day 1 (start of the administration of the first infusion). The duration of the DLT windows and definition of DLT-evaluable subjects are shown below ([Table 6-2](#)).

All available safety data for subjects who are not DLT evaluable will still be evaluated and considered in DLRT recommendations.

A DLT will be defined as any of the events described above occurring in a subject during the DLT window excluding events clearly related to disease progression or intercurrent illness. The CTCAE version 5.0 (see Section 11.4) will be used to grade adverse events.

